25. LOCAL NUMBER OF SUBJECTS

Phase 1 Aim 1 (Develop OARSCM): 30 individuals with OUD and 30 providers/clinicians will be recruited to provide feedback to improve the interface and features.

Phase 2 Aims 1 & 2 (RCT of OARSCM): 102 patients will be enrolled and randomized into OARS+CM (n=51), or TAU with MyMAT (n=51) to determine efficacy of OARSCM. See grant: "RESEARCH STRATEGY" (p12) "Procedures" for further details.

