Statistical Design and Power

Data analyses will proceed with the intent-to-treat sample. Initial analyses will compare groups on baseline and demographic variables using chi-square test (for categorical variables) and analysis of variance (for continuous variables). Variables that significantly differ between groups or are theoretically important, such as pain and other (non-opioid) substance use disorder will be used as covariates in multivariate analysis, when appropriate. For end-of-treatment outcomes, analysis will compare groups via chi-square, Kruskal-Wallis test, and analysis of variance (ANOVA) or analysis of covariance (ANCOVA) tests, as appropriate. Evaluation of changes in outcomes through the follow-up period will occur with hierarchical mixed models specified for dichotomous or continuous outcomes (PROC MIXED and PROC GLIMMIX SAS procedures). These analyses allow for intra-subject serial correlation, unequal variance and covariance structures, and unequally spaced assessment intervals. They also account for missing data by using all available data and maximum likelihood estimation of parameters. To use the mixed effect modeling analysis in assessing intervention effect, an interaction term (intervention group by time) will be included together with other covariates (e.g., age, ethnicity, chronic pain, anxiety, trauma history, utilization of psychiatric or medical services). A significant beta coefficient of the interaction term at $p < .05$ level will be used as evidence supporting the intervention effect. Analysis of change scores can analyze variables that cannot be normalized. For all analyses, effect sizes will be estimated, with parametric and non-parametric statistics as appropriate; effect sizes for effects by sex will be estimated. Statistical significance will be at $p < .05$ and analyses will occur via IBM® SPSS® Statistics V21 and SAS 9.4 statistical software package (SAS Institute Inc, Cary, NC).

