Aim 3 is to evaluate costs. Economic evaluation of the CM intervention is highly relevant to considerations of implementation and will be informed by expert guidelines.¹⁵⁹ The primary hypothesis is that the incremental cost-effectiveness (cost per participant who does not have repeat OUD-related emergency acute care, measured at the end of treatment and the last follow-up) will be acceptable and support sustainability. The study will also determine the incremental cost of the CM intervention per OUD patient treated, to identify the budget impact of adoption on a large-scale basis if the intervention is efficacious. For analyses, we will determine the Incremental Cost Effectiveness Ratio (ICER) in dollars per repeat acute care visit averted. This ratio is the difference in cost incurred by the OARS+CM group divided by the difference in the proportion of participants without repeat acute care services over the short (intervention period) and long term (last follow-up). The statistical uncertainty of the incremental cost-effectiveness will be estimated by bootstrap analysis of trial data, a method that preserves the covariance between costs and outcomes.¹⁶⁰ A cost-effectiveness acceptability curve will be plotted with the proportion of replicates that are cost-effective at different threshold values of willingness to pay per successful quit participant.¹⁶¹ The p -value for the statistical test that the OARS+CM intervention is cost-effective will be found by determining the proportion of replicates that are above each threshold value. We will conduct a literature review of cost-effectiveness studies to identify likely threshold values of dollars per OUD person treated in general. Costs of activities that are solely for research purposes (weekly surveys, follow-ups) will be excluded. Also see the Commercialization Plan for our approach to cost-savings and cost-avoidance.

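### Aim 3 (exploratory): read literally, the p-value rule for cost-effectiveness counts bootstrap replicates in which OARS+CM costs more and works worse as support for it

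*SAP*

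**What the plan says.** The Aim 3 paragraph of the SAP defines the ICER as a plain quotient: "This ratio is the difference in cost incurred by the OARS+CM group divided by the difference in the proportion of participants without repeat acute care". Two horizons are named, the intervention period and last follow-up. On uncertainty it says: "The statistical uncertainty of the incremental cost-effectiveness will be estimated by bootstrap analysis of trial data".

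Two uses of the replicates follow. The first is graphical: "A cost-effectiveness acceptability curve will be plotted with the proportion of replicates that are cost-effective at different threshold values of willingness to pay". The paragraph does not say what makes a replicate cost-effective. The second is the p-value for the claim that OARS+CM is cost-effective, which "will be found by determining the proportion of replicates that are above each threshold value".

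The thresholds are not fixed: "We will conduct a literature review of cost-effectiveness studies to identify likely threshold values of dollars per OUD person treated in general". No significance level is set for this aim. The general level of 0.05 in the SAP's Statistical Design and Power section is the only one available, and sidedness is not stated. The SAP gives Aim 3 a primary hypothesis that the ratio will be acceptable, whereas section 4 of the protocol describes the cost data as exploratory. Section 25 of the protocol gives 51 participants per arm.

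**The concern.** A small p-value is meant to support cost-effectiveness, so a replicate that is not above the threshold counts in favour. The threshold is in dollars of willingness to pay, and the quantity that the paragraph defines and bootstraps is the ratio. Comparing the two makes sense only when the denominator is positive. Once the effect difference is negative, the sign of the ratio no longer separates good from bad, and its size runs the wrong way.

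The costlier-and-worse quadrant matters most, because OARS+CM adds prizes to usual care and a higher cost is plausible. If the effect were null or adverse, the rule as written could yield a small p-value for an intervention that the same data show to be poor value. That p-value bears on whether the cost is called acceptable and sustainable.

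**Working it through.** The SAP states no Aim 3 figure (no power, threshold, expected cost or event rate), so there is nothing to reproduce. The check is algebra first, then an illustration.

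**Notation.** ΔC is the cost difference (OARS+CM minus control), ΔE is the difference in the proportion without repeat acute care, and λ is the threshold.
- Rule as written: p = share of replicates with ΔC/ΔE > λ.
- Net benefit: NB = λ × ΔE − ΔC, and p = share of replicates with NB ≤ 0.

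**Step 1: single replicates at λ = $5,000 (invented values, to show the signs).**

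| ΔC | ΔE | Ratio | Rule as written | NB | Correct direction |
|---|---|---|---|---|---|
| +300 | −0.20 | −1,500 | for | 5,000 × (−0.20) − 300 = −1,300 | against |
| −300 | −0.02 | +15,000 | against | 5,000 × (−0.02) + 300 = +200 | for |
| −300 | −0.20 | +1,500 | for | 5,000 × (−0.20) + 300 = −700 | against |

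When ΔE > 0, ΔC/ΔE > λ is the same statement as NB < 0, so the two rules agree. When ΔE < 0, dividing by ΔE reverses the inequality.

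**Step 2: inputs for an illustration.** From the documents: 51 per arm. Assumed: 60% without repeat acute care under control, $300 mean extra cost, cost SD $300 (also $1,500 and $5,000), cost uncorrelated with effect, λ = $5,000.

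**Step 3: hand calculation at cost SD $300.** The standard error of ΔC is 300 × √(2/51) = $59, which is 59/5,000 = 0.012 on the effect scale and can be ignored here. With ΔC near $300, the ratio exceeds $5,000 only if 0 < ΔE < 300/5,000 = 0.06, while NB ≤ 0 whenever ΔE ≤ 0.06. The two p-values therefore differ by P(ΔE ≤ 0). The standard error of ΔE is √[p₀(1−p₀)/51 + p₁(1−p₁)/51].

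| Without repeat care, OARS+CM vs control | SE(ΔE) | Net-benefit p = P(ΔE ≤ 0.06) | P(ΔE ≤ 0) | Written-rule p |
|---|---|---|---|---|
| 40% vs 60% | 0.097 | Φ(2.68) = 0.996 | Φ(2.06) = 0.980 | 0.016 |
| 60% vs 60% | 0.097 | Φ(0.62) = 0.73 | 0.50 | 0.23 |
| 70% vs 60% | 0.094 | Φ(−0.43) = 0.335 | Φ(−1.06) = 0.143 | 0.19 |
| 80% vs 60% | 0.089 | Φ(−1.58) = 0.057 | Φ(−2.26) = 0.012 | 0.045 |

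**Step 4: simulated trials, 1,000 bootstrap replicates each.** Median p at λ = $5,000, cost SD $300:

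| True effect of OARS+CM | Written rule | Net benefit |
|---|---|---|
| none | 0.21 | 0.74 |
| 10 points better | 0.18 | 0.32 |
| 20 points better | 0.045 | 0.053 |

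Share of trials with p<.05 under the written rule when OARS+CM is 20 points worse; net benefit gives about 0% at λ = $5,000 for all three SDs:

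| Cost SD | λ = $1,000 | λ = $5,000 | λ = $20,000 |
|---|---|---|---|
| $300 | 63% | 67% | 83% |
| $1,500 | 32% | 63% | not tabulated |
| $5,000 | 7% | 24% | not tabulated |

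These percentages carry simulation error of a few points.

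**The case against.** The strongest reply is that this holds the authors to a loose sentence. The sentence just before it speaks of replicates that are cost-effective, and a costlier, less effective replicate is not cost-effective in any ordinary sense. The p-value sentence may be shorthand for the complement of that curve, or for lying above the threshold line on the cost-effect plane; on either reading the test is sound. The paragraph also cites guidance and methods papers that may specify the scoring. This stands as a caution about intent. It does not repair the text: the curve sentence leaves its key term undefined, the p-value sentence is the only operational rule given, and the cited sources cannot be checked here.

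Second, Aim 3 is exploratory in the protocol, with no fixed threshold and no significance level of its own. The ICER would be reported beside the p-value, so an adverse effect could be seen, and the budget-impact work is conditional on efficacy. This stands. A reader might take the rule for a success criterion of the trial; the documents do not support that.

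Third, a reader might infer that 51 per arm makes negative effect differences common in the replicates whatever the truth. That holds mainly when the effect is null or adverse. In the hand calculation the share is about 50% with no effect and 98% at 20 points worse, but about 1% at 20 points better.

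Fourth, the size rests on assumed inputs, above all the cost SD. If acute-care costs enter ΔC, the SD could be well above $300, and costs would be correlated with the effect, which was not modelled. This also stands, and is why a range is shown.

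**Conclusion.** The point holds as a defect in the wording of an exploratory analysis. Read literally against the ratio that the SAP defines, the p-value rule is valid only for positive effect differences. That conclusion is algebraic and needs no assumed figures.

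How much it matters depends on inputs that the documents do not give. Under the assumptions above, the distortion is large when OARS+CM is worse (about 24% to 67% of trials wrongly reaching p<.05 at a $5,000 threshold as the cost SD falls from $5,000 to $300). It is material when there is no effect or a modest benefit, and negligible on the p-value scale when there is a clear benefit.

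A reader might go further and infer that the trial will declare a harmful intervention cost-effective, or that the analysts intend to count such replicates in favour. Neither follows. The first needs an adverse effect that nothing in the documents predicts; the second attributes an intention to a sentence that may only be incomplete. The change is worth making before analysis, but the main efficacy comparisons do not depend on it.

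**What to change.** Replace the p-value sentence in the Aim 3 paragraph, and define the term used in the curve sentence, as follows:

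- For each replicate and threshold, compute the net monetary benefit: threshold × (difference in proportion without repeat acute care) − (difference in cost). Call the replicate cost-effective if this exceeds 0.
- Take the p-value at each threshold as the proportion of replicates with net benefit ≤ 0, and plot the acceptability curve as its complement.
- Report the share of replicates in each quadrant of the cost-effect plane beside the ICER.

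The threshold should be expressed in dollars per additional participant without repeat acute care, so that the product is in dollars.

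The cost is a few sentences in the SAP. The same bootstrap replicates are used, no new data are needed, and if the analysts already intended net benefit or the threshold line, nothing changes except that the plan says so.
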